12. ADVERSE EVENTS, SERIOUS ADVERSE EVENTS, AND REPORTING

12.1. ADVERSE EVENTS

12.1.1. Definition

An AE is defined as any untoward medical occurrence in a clinical investigation subject administered a pharmaceutical product and which does not necessarily have a causal relationship with the treatment. An AE can therefore be any unfavorable and unintended sign, symptom, or

disease temporally associated with the use of a medicinal (investigational) product, whether or not related to that product. An AE can arise with any use (eg, in combination with another drug), route of administration, formulation, or dose, including an overdose.

Possible AEs associated with TransCon hGH are listed in the Investigator's Brochure or the accompanying Reference Safety Information. The adverse reactions associated with commercially available daily hGH-containing products that may or may not be observed with use of TransCon hGH are:

- Sudden death in pediatric patients with Prader-Willi syndrome; risk factors include morbid obesity, history of upper airway obstruction or sleep apnea, and unidentified respiratory infection
- Intracranial tumors, particularly meningiomas, in teenagers/young adults treated with brain irradiation as children
- Injection site reactions/rashes (as well as rare, generalized hypersensitivity reactions)
- Skin atrophy and lipoatrophy
- **Note:** Rotating the injection site (see Section 9.3) is expected to decrease the risk of skin atrophy or lipoatrophy.
- Headaches
- Glucose intolerance, including impaired glucose tolerance/impaired fasting glucose as well as overt diabetes mellitus
- Intracranial hypertension with papilledema, visual changes, headache, nausea, and/or vomiting
- Fluid retention manifested by edema, arthralgia, myalgia, nerve compression syndromes (including carpal tunnel syndrome/paresthesias)
- Hypothyroidism (central [secondary] hypothyroidism may first become clinically evident or worsen in patients with GHD during hGH treatment)
- Slipped capital femoral epiphysis (occurs more frequently in patients with endocrine disorders or in patients undergoing rapid growth)
- **Note:** Any subject with the onset of a limp or complaints of hip or knee pain should be carefully evaluated for a slipped capital femoral epiphysis.
- Progression of pre-existing scoliosis due to rapid growth (hGH has not been shown to increase the occurrence of scoliosis)
Note: Any subjects with a history of scoliosis should be monitored for progression of scoliosis.
- Pancreatitis - Cases of pancreatitis have been reported rarely in children and adults receiving hGH treatment, with some evidence supporting a greater risk in children compared with adults. Pancreatitis should be considered in any hGH-treated subject, especially a child, who develops persistent severe abdominal pain.

AEs may include:

- Clinically significant treatment-emergent physical examination abnormalities
- Out-of-range lab or test results associated with new/worsening diagnosis, clinical sign, or symptom; or that require therapy

In this trial, all AEs that are considered mild and not related to investigational product will not be recorded on the AE CRF; this is with the exception of site-specific reporting preferences. In addition, the following out-of-range laboratory values—whether or not associated with a titration of the TransCon hGH dose—will not be considered AEs unless they are associated with a sign or symptom: IGF-1, IGF-1 SDS, IGFBP3, IGFBP3 SDS. In this trial, IGF-1 and IGFBP3 are pharmacodynamic markers of TransCon hGH therapy and may be used to guide an investigator's recommendation to titrate the TransCon hGH dose.

The Medical Expert will review all safety information on an ongoing basis. The key safety data will also be reviewed periodically by an ISC in accordance with its governing charter.

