6. OBJECTIVES

6.1. PRIMARY OBJECTIVE

To assess long-term safety of weekly TransCon hGH in children with GHD previously treated in a phase 3 TransCon hGH trial

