12.1.3. Reporting Procedures for All Adverse Events

At each visit, all AEs will be documented in response to a general question about the subject's well-being and whether any possible changes in well-being have occurred since the previous visit. Additionally, at each visit, site staff will review subject diary data with the subject and parent/legal guardian/caregiver, to determine if diary entries reflect any AEs. There will be no direct questioning to solicit possible AEs. AEs reported up to 14 days after the final dose of TransCon hGH will be captured. AEs, including SAEs, will be documented through the end of the subject's participation in the trial. All AEs ongoing at the completion of the study or Early Termination Visit must be followed until the event is resolved or deemed stable by the investigator. In this trial, all AEs that are considered mild and not related to investigational product will not be reported on the AE CRF. In addition, the following out-of-range laboratory values—whether or not associated with a titration of the TransCon hGH dose—will not be considered AEs unless they are associated with a clinical sign or symptom: IGF-1, IGF-1 SDS, IGFBP3, IGFBP3. In this trial, IGF-1 and IGFBP3 are pharmacodynamic markers of TransCon hGH therapy and may be used to guide an investigator's recommendation to titrate the TransCon hGH dose. Reportable AEs must be recorded on the appropriate eCRF. Reportable AEs either observed by the investigator or reported by the subject must be recorded regardless of causality.

The following attributes must be documented for each reported AE:

- Subject ID
- Description

- Onset date (if AE was present on Day 1, include whether onset was prior to or after first dose of investigational product)
- Resolution date, if applicable
- Severity
- Causality (relationship to investigational product)
- Outcome
- Action taken
- Determination of “serious” (or not)

Any ongoing AEs from the prior trial will be followed until resolution or stabilization. Any changes to the conditions documented as medical history during the trial and that meet the above AE definition should be recorded as AEs so that a complete safety profile of the investigational product is obtained. See Section 12.2.2 for additional reporting procedures for serious AEs.

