14.1. TRIAL ENDPOINTS

14.1.1. Safety Endpoints

The safety endpoints as measured throughout the long-term dosing of weekly TransCon hGH treatment include the following:

- Incidence of AEs
- Incidence of antibodies against hGH, including neutralizing antibodies
- Incidence of antibodies against PEG
- Incidence of antibodies against TransCon hGH
- Incidence of IGF-1 SDS > 2.0, > 3.0
- Parameters of HbA1c and lipids
- Hormone levels, including thyroid status and morning cortisol
- All other hematology and chemistry parameters
- Vital sign measurements

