- ¹¹ For subjects who were treated with Genotropin in the prior TransCon hGH CT-301 trial, C&OS-P, CSDS-P, CSDS-C, PQ-P, and PQ-C will be completed (as applicable) within the subject diary immediately prior to the 6th dose of investigational product, and in clinic at Visit 2, prior to review of the subject diary, AEs, and concomitant medications. For subjects transitioning to the GH Auto-Injector, C&OS-P, CSDS-P, and CSDS-C will be completed (as applicable) within the subject diary immediately prior to the 6th dose after transition to the GH Auto-Injector, and again in clinic at the following scheduled visit, prior to review of the subject diary, AEs, and concomitant medications. Additionally, for subjects transitioning to the GH Auto-Injector, the DUQ will be completed within the subject diary on the day of the 6th dose of investigational product, and in clinic at Visit 2, prior to review of the subject diary, AEs, and concomitant medications.
- ¹² CSDS-C and PQ-C should only be completed by subjects \geq 9 years old at the time of Visit 1, and/or at the transition to the GH Auto-Injector, as applicable.
- ¹³ Dose adjustments at visits are typically based on subject weight at visits. However, dose adjustments may occur between visits per Section 9.6.
- ¹⁴ Local tolerability assessment at the injection site to be performed at time of injection, and by the trial staff at visits.
- ¹⁵ Investigational product compliance includes review of subject diary and returned investigational product.
- ¹⁶ AE review includes review of subject diary and physical examination of injection sites. AEs that are considered mild and not related to investigational product will not be reported on the AE CRF. AEs reported up to 14 days after the final dose of TransCon hGH will be captured.

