- 11 For subjects who were treated with Genotropin in the prior TransCon hGH CT-301 trial, C&OS-P, CSDS-P, CSDS-C, PQ-P, and PQ-C will be completed (as applicable) within the subject diary immediately prior to the 6th dose of study drug, and in clinic at Visit 2, prior to review of the subject diary, AEs, and concomitant medications. For subjects transitioning to the auto-injector, C&OS-P, CSDS-P, and CSDS-C will be completed (as applicable) within the subject diary immediately prior to the 6th dose after transition to the TransCon hGH auto-injector, and again in clinic at the following scheduled visit, prior to review of the subject diary, AEs, and concomitant medications.
- 12 CSDS-C and PQ-C should only be completed by subjects ≥ 9 years old at the time of Visit 1, and/or at the transition to the TransCon hGH auto-injector, as applicable.
- 13 Dose adjustments at visits are based on subject weight at visits. However, dose adjustments may occur between visits per Section 9.6.
- 14 Local tolerability assessment at the injection site to be performed at time of injection, and by the trial staff at visits.
- 15 Study drug compliance includes review of subject diary and returned study drug.
- 16 AE review includes review of subject diary and physical examination of injection sites. AEs that are considered mild and not related to study drug will not be reported on the AE CRF.

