8.1. Adverse Events

AE is defined as any untoward medical occurrence in a clinical investigation subject administered a pharmaceutical product and which does not necessarily have a causal relationship with the treatment. An AE can therefore be any unfavorable and unintended sign (including

abnormal laboratory finding), symptom, or disease temporally associated with the use of a medicinal (investigational) product, whether or not related to that product. An AE can arise with any use (e.g., in combination with another drug), route of administration, formulation, or dose, including an overdose.

An AE is considered treatment emergent, i.e., Treatment Emergent Adverse Event (TEAE), is any AE that was first occurred or worsened after the first dose in this extension study and before the end of study. If the AE has any missing start date, the rules stated in Section 5.2 will be applied to determine if it is treatment-emergent.

A serious AE (SAE) is SAE is any untoward medical occurrence that:

- Results in death
- Is life-threatening
- Requires inpatient hospitalization or prolongation of an existing hospitalization
- Results in persistent or significant disability/incapacity
- Is a congenital anomaly/birth defect

Summaries of incidence rates (frequencies and percentages) of individual TEAEs by MedDRA SOC and preferred term will be prepared. Such summaries will be displayed for all TEAEs, TEAEs by maximum intensity, and TEAEs by strongest relationship to study drug. In addition, related TEAE, non-related TEAE, TEAE leading to study drug discontinuation, and serious TEAE, by SOC, the preferred term and TEAE by preferred term will be also summarized. Especially, related includes definite, probable and possible relationship. Not-related includes unlikely/remote and unrelated/not related.

Each subject will be counted only once within each preferred term. If a subject experience more than one TEAE within a preferred term, only the TEAE with the strongest relationship or the maximum intensity, as appropriate, will be included in the summaries of relationship and intensity.

Data listing of AEs, TEAE leading to study drug discontinuation, serious TEAE will also be provided.

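### Recording of mild, unrelated AEs is partly left to site preference, so the all-TEAE, mild-intensity and non-related tables in SAP 8.1 mix recording rules

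*Protocol*

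**What the plan says.** The recording rule appears in four places, and only one carries an exception.

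- Protocol 12.1.1: mild, unrelated AEs "will not be recorded on the AE CRF; this is with the exception of site-specific reporting preferences".
- Protocol 12.1.3: "all AEs that are considered mild and not related to investigational product will not be reported on the AE CRF".
- Protocol 18.2, Schedule of Events, footnote 16: "AEs that are considered mild and not related to investigational product will not be reported on the AE CRF".
- SAP Table 1 (under section 3.2), footnote 16: "AEs that are considered mild and not related to study drug will not be reported on the AE CRF".

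The Version 2.0 summary of changes lists the site exception as a deliberate addition. The SAP overview names Protocol 1.0 as the version it describes.

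On analysis, the first-listed safety endpoint in Protocol 14.1.1 is "Incidence of AEs", under the primary objective in 6.1: "To assess long-term safety of weekly TransCon hGH in children with GHD previously treated in a phase 3 TransCon hGH trial". SAP 8.1 plans incidence tables by SOC and preferred term: "Such summaries will be displayed for all TEAEs, TEAEs by maximum intensity, and TEAEs by strongest relationship to study drug". It adds separate tables for related, non-related and serious TEAEs, among others. For those tables, "Not-related includes unlikely/remote and unrelated/not related". Protocol 12.1.2.2, by contrast, keeps *Unlikely* and *Unrelated/Not Related* as two causality categories.

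**The concern.** Whether a mild, unrelated event enters the database depends on the site. The documents do not say which sites may use the exception, whether the choice is logged, or whether it must stay the same over time. SAP 8.1 has no filter to a common recording rule, no flag for sites using the exception and no sensitivity table. Under Protocol section 14 the SAP is the analysis of record, so nothing else fills the gap.

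The trial has no concurrent control, so the TEAE percentages are themselves the safety result. An all-TEAE percentage built from two recording rules is neither the incidence of all AEs nor the incidence of a defined subset. A contrast between groups that come from different sites can then reflect recording practice rather than safety.

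**Working it through.** **Which displays are affected.** The exclusion removes events that are both mild and not related.

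| Display in SAP 8.1 | Can an event be missing at some sites only? |
|---|---|
| All TEAEs, overall and by SOC/PT | Yes |
| Mild row of the maximum-intensity table | Yes |
| Non-related TEAEs | Yes |
| Related TEAEs (definite, probable, possible) | No |
| Moderate and higher rows | No |
| Serious TEAEs | Largely no: Protocol 12.2.2 requires SAE reporting whatever the causality |

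**Which contrasts are exposed.** SAP 3.1 defines three groups by parent study and treatment.

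- CT-302 against CT-301 rollover subjects is exposed, because the two trials recruited separately and their site mix may differ.
- US against non-US is exposed, but SAP 9.4 makes this summary optional.
- The two CT-301 arms are less exposed: Protocol 5.3 describes them as randomised 2:1 within one trial, so they share a pool of sites.

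**Size.** The plan gives no AE rate, so there is no figure to reproduce. Let

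- p = share of subjects with at least one AE that every site records,
- q = share whose only AEs are mild and unrelated,
- f = share of subjects at sites that record such events.

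If p and q are the same at both kinds of site, observed incidence = p + f × q. All three inputs are assumptions.

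With p = 0.40 and q = 0.30:

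| f | p + f × q |
|---|---|
| 0 | 40% |
| 0.10 | 43% |
| 0.25 | 47.5% |
| 0.50 | 55% |
| 1 | 70% |

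The excess is f × q and does not involve p. Over q = 0.20 to 0.40:

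- f = 0.10 adds 2 to 4 points.
- f = 0.50 adds 10 to 20 points.
- Two groups with equal true rates but f = 0.10 and 0.50 differ by 0.40 × q = 8 to 16 points.

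For scale, the 95% half-width for a proportion of 0.5 with the planned 300 subjects is 1.96 × √(0.25/300) = 5.7 points. The excess reaches that size when f = 0.057/q, that is f ≈ 0.28, 0.19 and 0.14 for q = 0.20, 0.30 and 0.40.

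**Which set is common to all sites.** A site that reads *not related* as SAP 8.1 does would leave out mild *Unlikely* events. A site that uses the protocol's separate categories would record them. A filter that keeps mild *Unlikely* events would therefore still mix practices. Among mild non-serious events, only those rated possible, probable or definite are recorded under either reading. Restricting to that set, plus moderate-or-worse and serious events, gives p whatever the value of f.

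**The case against.** Protocol 12.1.1 makes non-recording the default, and the exception may be used at few sites; at f = 0.10 the excess is below the sampling half-width. The analysis is descriptive, with no test, margin or power calculation. The displays that carry most safety weight are already planned and largely untouched. The SAP also states the exclusion in its own footnote, so it does not claim that its tables cover all AEs. Keeping every recorded event in the main safety display is a legitimate choice.

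Most of this stands, and it limits the point. It does not remove it: the SAP footnote describes one rule, while current Protocol 12.1.1 permits two.

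A reader might infer that the trial's AE incidence is unreliable as a whole, or that every comparison between rollover groups reflects recording practice. The documents do not support either. The mixing is confined to three kinds of table, and the CT-301 arms share sites. Nor do the documents show that the effect is large, because they give neither the number of sites using the exception nor the rate of mild unrelated AEs.

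**Conclusion.** The point holds in limited form. The four statements of the recording rule disagree, and the SAP does not reflect the exception added in Version 2.0. Following the plan as written gives all-TEAE, mild-intensity and non-related incidences that depend on which sites use the preference and how many subjects they contribute. The rule may also have changed over calendar time when Version 2.0 took effect.

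The size is unknown. The 10 to 20 points rest on assumed q = 0.20 to 0.40, a rise in f from 0 to 0.50, and equal true rates at both kinds of site; with few such sites the effect would be small. The unclear status of mild *Unlikely* events is a second possible source of variation between sites. The correction is cheap and concerns a safety endpoint under the primary objective, so it should be made.

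**What to change.** In SAP 8.1:

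1. Add a TEAE incidence table (overall, by SOC and preferred term, by group) restricted to events that are moderate or worse, or possibly, probably or definitely related, or serious. Use it for any between-group or regional comparison.
2. Keep the all-recorded TEAE table, with a title stating that mild unrelated events were not systematically collected. Which of the two is called the main table is a matter of preference.

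In the protocol and SAP:

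3. Reconcile Protocol 12.1.1, 12.1.3 and Schedule of Events footnote 16 with SAP Table 1 footnote 16 on the site exception. If it stays, log which sites use it and from when.
4. State whether a mild *Unlikely* event counts as not related for recording, and that serious events always go on the AE CRF.

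The analysis part costs one filter on existing data and one extra set of tables. The restricted incidence may be materially lower than the all-recorded figure: 40% against 55% in the illustration at f = 0.50. The protocol clarification needs an amendment under Protocol 15.9 and does not repair data already collected.

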12.1.2. Severity, Causality, and Outcome Assessment

12.1.2.1. Severity Rating

The following guideline must be used by the investigator to grade the intensity of an AE:

Mild – The subject is aware of the sign or symptom but tolerates it easily. The event is of little concern to the subject and/or of little or no clinical significance. The event is not expected to have any effect on the subject's health or well-being. The event may or may not require medical intervention.

Moderate – The event causes the subject enough discomfort for it to cause interference with or change some of the subject's usual activities. The event is of some concern to the subject and poses some risk to the subject's health or well-being. The event may require medical intervention.

Severe – The subject is incapacitated and unable to work or participate in many or all usual activities. The event is of definite concern to the subject and/or poses substantial risk to the subject's health or well-being. The event is likely to require medical intervention and/or close follow-up.

Life-threatening – The subject is at immediate risk of death from the event as it occurred.

12.1.2.2. Causality Rating

The principal investigator will assess the causal relationship between the investigational product and the event using the following guideline:

Definite – This causality category applies to those AEs which the investigator feels are clearly related to the investigational product. An AE may be categorized as definitely related to the investigational product when the event meets the first 4 (or more) of the following criteria:

- The event follows a reasonable temporal sequence from investigational product administration

- The event cannot be reasonably explained by known characteristics of the subject's clinical status, environmental or toxic factors, or other therapies administered
- The event disappears or decreases in severity upon cessation of the investigational product. [There are important exceptions when an AE may not disappear upon discontinuation of the drug, yet drug-relatedness clearly exists (eg, tardive dyskinesia)]
- The event follows a known response pattern to the investigational product
- The event reappears upon re-challenge (if applicable)

Probable – This causality category applies to those AEs which the investigator feels a high degree of certainty are related to the investigational product. An AE may be categorized as probably related to the investigational product when the event meets the first 3 (or more) of the following criteria:

- The event follows a reasonable temporal sequence from investigational product administration
- The event cannot be reasonably explained by known characteristics of the subject's clinical state, environmental or toxic factors, or other therapies administered
- The event disappears or decreases in severity upon cessation of the investigational product. [There are important exceptions when an AE may not disappear upon discontinuation of the drug, yet drug-relatedness clearly exists (eg, tardive dyskinesia)]
- The event follows a known response pattern to the investigational product
- The event reappears upon re-challenge (if applicable)

Possible – This causality category applies to those AEs in which the investigator feels there is a reasonable, although not probable, connection with the investigational product. An AE may be categorized as possibly related to the investigational product when the event meets the first 2 (or more) of the following criteria:

- The event follows a reasonable temporal sequence from investigational product administration
- The event is possibly explained by known characteristics of the subject's clinical state, environmental or toxic factors, or other therapies administered to the subject
- The event follows a known response pattern to the investigational product

Unlikely – This causality category applies to those AEs in which the investigator feels there is unlikely a connection with the investigational product. An AE may be categorized as unlikely related to the investigational product when the event meet the first 2 (or more) of the following criteria:

- The event does not follow a reasonable temporal sequence from investigational product administration
- The event may readily be explained by known characteristics of the subject's clinical state, environmental or toxic factors, or other therapies administered to the subject

- The event does not follow a known response pattern to the investigational product

Unrelated/Not Related – This category is applicable to those AEs in which the investigator feels there are clearly extraneous causes (disease, environment, etc.) and do not meet the criteria for drug relationship listed under Definite, Probable, Possible, or Unlikely, as noted above.

